11.4.3 Medical History and Prior Medication

Medical history and prior medication information before the first study medication will be summarized by treatment group using relative frequencies in open-label / Japan open-label extension / long-term extension treated analysis populations. Listings of medical history and prior medication will be presented by treatment group in the open-label / Japan open-label extension / long-term extension treated analysis populations.

11.5 Extent of Exposure

11.5.1 Study Therapy

Extent of exposure to study drug in the open-label / Japan open-label extension / long-term extension treated analysis populations will be summarized in two ways; first, by the number of abatacept injections, summarizing frequency distribution of number of abatacept injections taken by treatment group, and second, by the number of days (or months) the subject is known to be on abatacept, ignoring any dosing interruptions. Exposure will be presented separately for the open-label / open-label extension / long-term extension periods and the cumulative abatacept period.

11.5.1.1 Open-Label Period Exposure

The extent of exposure for the open-label period will be calculated and presented in days as follows:

- For subjects who discontinued during the open-label period or did not enter the open-label extension period or the long-term extension period within 56 days of the last injection in the open-label period:
- Exposure in days = (date of last injection in the open-label period - date of first open-label injection + 1) + 56.

For subjects who enter open-label extension or long-term extension period within 56 days of the last injection in the open-label period:

- Exposure in days = (date of first injection in the open-label extension or long-term extension period - date of first open-label injection).

The offset of 56 days is the length of 2 regular dosing cycles and represents approximately 4 times the half-life of Abatacept in humans.

Summaries of exposure to study drug will show the distribution of the number of injections and days on drug, together with the means, standard deviations, medians, minima and maxima, by treatment group.

11.5.1.2 Open-Label Extension Period Exposure

The extent of exposure for the open-label extension period will be calculated and presented in days as follows:

- For subjects who discontinued during the open-label extension period or did not enter the long-term extension period within 56 days of the last injection in the open-label extension period:
- Exposure in days = (date of last injection in the open-label extension period - date of first open-label extension injection + 1) + 56.

For subjects who enter long-term extension period within 56 days of the last injection in the open-label extension period:

- Exposure in days = (date of first injection in the long-term extension period - date of first open-label extension injection).

11.5.1.3 Long-Term Extension Period Exposure

The extent exposure of for the long-term extension period will be calculated and presented in days as follows:

Exposure in days = (date of last injection in the long-term extension period - date of first long-term extension injection + 56).

11.5.1.4 Cumulative Abatacept Exposure

The cumulative abatacept exposure will only be computed for the final analysis (i.e. at the study closeout); the exposure to abatacept during the cumulative period will be calculated as follows:

Exposure in months = (date of last dose of abatacept in the study - date of first dose of abatacept in the study + 1 - adjustment + 56)/30.

The offset of 56 days represents approximately 4 times the half-life of abatacept in humans.

Adjustment is the sum of the time span between:

- the last dose of abatacept in the double-blind period and the first dose of abatacept in the open-label period which exceeds 56 days (all sites),
- the last dose of abatacept in the open-label period and the first dose of abatacept in the open-label extension period which exceeds 56 days (Japan sites); or the last dose of abatacept in the open-label period and the first dose of abatacept in the long-term extension period which exceeds 56 days (all other sites but not including U.S. and Czech Republic sites),
- the last dose of abatacept in the open-label extension period and the first dose of abatacept in the long-term extension period which exceeds 56 days (Japan sites).

Summaries of cumulative period exposure to study drug will show the distribution of the number of months on drug, together with the means, standard deviations, medians, minima and maxima, by treatment group. A listing of abatacept study medication dose dates will also be provided for the cumulative period.

11.5.2 Discontinuation of Study Therapy

Discontinuation from study therapy is defined as a subject's termination of the study medication without resumption prior to study completion. The discontinuation from study therapy during the open-label / open-label extension / long-term extension periods will be summarized for all open-

label / open-label extension / long-term extension periods treated subjects, by treatment group and the reason for premature termination, taken from the subject status eCRF page.

11.5.3 Treatment Compliance

The number of subjects who missed study medication doses (excluding missed doses due to premature discontinuation from the study) during open-label / open-label extension / long-term extension will be summarized for all open-label / open-label extension / long-term extension periods treated subjects, by double-blind treatment group and number of study dose missed. A corresponding listing of all treated subjects with missed doses during the open-label / open-label extension / long-term extension periods will be provided.

11.6 Efficacy

All efficacy analyses for the open-label / open-label extension periods will be performed using the open-label / Japan open-label extension treated analysis population, unless otherwise specified. Over time (double-blind and open-label / open-label extension visits) analyses will be performed for all efficacy endpoints specified in the 24 week Analysis Plan. The analyses will be as observed with no imputation for any missing data. No p-values will be provided for any of the open-label analyses.

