6.3 Populations for Analyses

Efficacy endpoints will be summarized according to the Intent-to-Treat (ITT) population and safety endpoints will be summarized according to the as-treated analysis population. These populations are described briefly below along with other populations.

- **Intent-to-Treat Analysis Population:**

The Intent-to-Treat (ITT) analysis Population is defined to include all subjects randomized into the study for whom Case Report Form (CRF) data indicate that at least one dose of study medication (abatacept or placebo) is administered during the double-blind period.

All subjects who are randomized but never received study medication are to be excluded. Given the blinded nature of this study, it is reasonable to assume that subjects who discontinue prior to the receipt of study medication do so for reasons unrelated to study medication. Subjects are grouped according to the treatments to which they are randomized by IXRS.

ITT analysis population is also referred to as “All Randomized and Treated Subjects”.

- **As-Treated Analysis Population:**

The As-Treated analysis population contains all subjects for whom CRF data indicate that at least one dose of study medication was administered during double-blind period.

Subjects are grouped according to the treatments to which they are randomized, except in cases where information is available, which indicates that a subject receives a different treatment for the entire course of double-blind period. In this case, the subject will be presented by the treatment they actually received.

The As-Treated analysis population will also be referred as “All Treated Subjects”.

- **Per-Protocol Analysis Population:**

The Per-Protocol analysis population is defined as a subset of the ITT analysis population which excludes subjects who have relevant protocol deviations during the double-blind study period. Relevant protocol deviations are those protocol deviations that might affect the primary efficacy endpoint of the study. A programmable list of relevant protocol deviation criteria is included in [APPENDIX 1](#).

The analysis of the primary efficacy endpoint will be repeated in the Per-Protocol analysis population. The Per-Protocol analysis population will exclude subjects with at least 1 relevant protocol deviation.

- **Open-Label Treated Analysis Population:**

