The Open-Label treated analysis population will contain all subjects for whom CRF data indicate that at least one dose of study medication was administered during the open-label period. All Week 52 analyses will be performed using this population except otherwise specified.

- **Japan Open-Label Extension Treated Analysis Population:**

The Japan Open-Label Extension treated analysis population will contain all subjects from Japan for whom CRF data indicate that at least one dose of study medication was administered during the open-label extension period. All Week 76 analyses will be performed using this population except otherwise specified.

- **Long-Term Extension Treated Analysis Population:**

The Long-Term Extension treated analysis population will contain all subjects (except for U.S. or Czech subjects) for whom CRF data indicate that at least one dose of study medication was administered during the long-term extension period. All Year 3 (3.5 year in Japan subjects) analyses will be performed using this population except otherwise specified.

█ [REDACTED]

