7.5.2 Primary Efficacy Analysis

The primary comparison of proportion of subjects in IMACS DOI at Week 24 between the SC abatacept and placebo groups will be assessed using a logistic regression model. To account for randomization stratification, the logistic regression model will adjust for the randomization stratification variables of disease diagnosis (DM vs. Non-DM), Interstitial Lung disease status (present vs. absent), and Japan vs. ROW; baseline MMT8 score, baseline MDAAT, baseline PGA and treatment group will also be included in the model. Point estimates of the adjusted Odds Ratios (OR) of the odds of achieving IMACS DOI in the abatacept group compared to the placebo group, corresponding 95% CI and p-value will be provided. Point estimates of the proportion of subjects in IMACS DOI in each treatment group and corresponding 95% CI will also be provided. All subjects who discontinue study medication prematurely prior to reaching the Week 24 assessment visit and/or received rescued medication at any time during the 24 week double-blind period, will be considered as not achieving IMACS DOI for the primary analysis. Efficacy assessments collected at Week 24 on subjects who discontinue study medication prior to Week 24 will not be included in the primary analysis of the primary endpoint, but will be included in a sensitivity analysis of the primary endpoint. Details of imputation rules for classification of IMACS DOI response for subjects with missing components of IMACS are provided in [Section 8.1.9](#). A table summarizing the number of imputed values for the primary endpoint by treatment group and missing data pattern will be provided. A summary of number of missing IMACS core measure item by treatment group will also be provided for subjects whose IMACS data are missing at Week 24 because of missing component data.

The primary estimand of the treatment difference in the proportion of subjects with IMACS DOI at Day 169 is the odds ratio (abatacept versus placebo) in the ITT analysis population that would be observed if all subjects who prematurely discontinued or received rescue medication before Day 169 or had missing IMACS DOI data would be non-responders.

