missing visit. Else, if a non-response is observed at one of the visits or a response is missing at one of the visits then a non-response will be imputed. If the given visit is the last scheduled efficacy visit (Day 169), the missing response will be imputed as non-response.

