11.6.1 Other Efficacy Analyses

IMACS DOI

Proportion of subjects in IMACS DOI over time during the study will be presented by the double-blind treatment groups and visit. Point estimate of response rate, 95% CI, point estimates and 95% CI of treatment difference adjusted for randomization stratification factors: disease diagnosis (DM vs. Non-DM), ILD (absent vs present), Region (Japan vs ROW) (based on minimum risk weights).

Proportion of subjects who meet the $\geq 20\%$ improvement from baseline over time for each of the core measures of IMACS (PGA, SGA, MMT-8, HAQ-DI, MDAAT and muscle enzymes) will be presented by double-blind treatment groups and visit. Point estimate of response rate, 95% CI, point estimates and 95% CI of treatment difference adjusted for randomization stratification factors: disease diagnosis (DM vs. Non-DM), ILD (absent vs present), Region (Japan vs ROW) (based on minimum risk weights).

The proportion of subjects in IMACS Minimal, Moderate and Major responses using the Myositis Response Criteria tool (as defined in [section 8.1.11](#)) will also be presented over time during the study. Point estimates and 95% CI within each treatment group for IMACS Minimal, Moderate and Major DOI response will be provided by visit. Differences in IMACS Minimal, Moderate and Major DOI response rates between the double-blind treatment groups will be provided by point estimate and corresponding 95% CIs based on an ordinal logistic regression model.

Additional separate longitudinal repeated mixed effects models will be used to assess the mean change from baseline over time in the study in each of the IMACS core measures (PGA, SGA, MMT-8, HAQ-DI, MDAAT and muscle enzymes). The mixed models will include double-blind treatment group, baseline measurement, randomization stratification factors: disease diagnosis (DM vs. Non-DM), ILD (absent vs present), Region (Japan vs ROW), time (study days in which each core measure was collected), time by baseline measurement and time by treatment interactions as fixed effects and subject as a random effect. Adjusted mean, SE, 95% CI for adjusted mean difference between treatment groups will also be provided. The estimate of baseline mean core measure, mean post-baseline core measure, and adjusted mean change from baseline core measure will be also be presented by double-blind treatment group and visit.

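### The Week 52 and Week 76 reports restate Week 24 IMACS DOI as observed, in a narrower population than the primary analysis, and their later rates can drift as subjects leave the denominator

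*SAP*

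**What the plan says.** **Primary analysis.** SAP 6.3 defines the intent-to-treat population as randomized subjects for whom "at least one dose of study medication (abatacept or placebo) is administered during the double-blind period". Under SAP 7.5.2, subjects who stop study medication before Week 24 or receive rescue "will be considered as not achieving IMACS DOI for the primary analysis". For a Day 169 status that cannot be evaluated for other reasons, SAP 8.1.9 says "the missing response will be imputed as non-response".

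**Later reports.** SAP Appendix 3, Section 11.6, sets the scope: "Over time (double-blind and open-label / open-label extension visits) analyses will be performed for all efficacy endpoints specified in the 24 week Analysis Plan". The population is the open-label treated set, for whom "at least one dose of study medication was administered during the open-label period", or its Japan extension counterpart for Week 76. The missing-data rule is "The analyses will be as observed with no imputation for any missing data". SAP 11.6.1 adds: "Proportion of subjects in IMACS DOI over time during the study will be presented by the double-blind treatment groups and visit", with a stratification-adjusted treatment difference and 95% CI. No p-values are planned.

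**What carries over.** Appendix 3 inherits SAP Sections 1 to 6 and Section 8 unless it states a change. Section 11.6 states one for missing data. It says nothing about rescue.

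**The concern.** One trial will produce two Week 24 DOI rates per randomized group, built on different populations and different rules, and the visible text does not reconcile them. The second rate conditions on having reached open label.

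That condition is unlikely to be neutral. Under Protocol 3.1.5, subjects who need a change of therapy for worsening before Week 12 must leave the study, as must those who fail rescue. Such subjects are failures in the primary analysis and absent from the Week 52 table.

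During open label, subjects who stop drop out of both numerator and denominator at each later visit. A response curve on a shrinking denominator can be read as growing benefit when nobody has newly responded. The Week 76 Japan report is the most exposed: it is small, it requires dosing in the extension, and SAP Section 1 says its purpose is to supply efficacy data for submission.

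**Working it through.** **Inputs.**
- From SAP Section 5: 75 per arm; planning DOI rates of 60% and 33%; two-sided 5%; continuity-corrected chi-squared test; power about 90%.
- Neither document states a dropout rate. I assume 7 leavers per arm (7/75 = 9.3%), borrowing the count of 7 missing used in the tipping-point grid of SAP 7.5.3.2, and show a range of 5% to 20%.

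**The plan's own figure.** The continuity-corrected effective size is (75 − 1/0.27)²/75 = 67.8 per arm, which gives 89.2% power. Exact enumeration of the corrected test gives 90.3%. The stated 90% reproduces, so the planning rates are a fair base for illustration.

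**Formulas.** Let R be responders under the primary rule, N the randomized and treated subjects, L those who leave, and k the responders among them. The primary rate is R/N. The as-observed rate is (R − k)/(N − L). It exceeds the primary rate only when k/L is below R/N.

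**Week 24, equal losses, all non-responders (k = 0).**
- Primary rule: 45/75 = 60.0% and 25/75 = 33.3%; difference 26.7 points.
- As observed, L = 7 per arm: 45/68 = 66.2% and 25/68 = 36.8%; difference 29.4 points.
- Range, dividing the planning rate by 1 − d: from 60%, 63.2% at d = 5% and 75.0% at d = 20%; from 33%, 34.7% and 41.2%. The shift is about 1.7 to 15 points.

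**Week 24, unequal losses (k = 0).**
- 4 abatacept, 11 placebo: 45/71 = 63.4% and 25/64 = 39.1%; difference 24.3 points.
- 11 abatacept, 4 placebo: 45/64 = 70.3% and 25/71 = 35.2%; difference 35.1 points.

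**Week 24, some leavers are responders.** With L = 7 on abatacept, k = 4 gives 41/68 = 60.3%, but k = 5 gives 40/68 = 58.8%, below the primary rate.

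**Later visits, responders held at 45 and 25, all leavers non-responders.**

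| Cumulative losses per arm | Abatacept | Placebo |
|---|---|---|
| 7 | 66.2% | 36.8% |
| 11 | 70.3% | 39.1% |
| 15 | 75.0% | 41.7% |
| 20 | 81.8% | 45.5% |

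The step from 60.0% to 66.2% is a difference in level between two reports, because subjects who never entered open label are missing from every visit of the later one. Only the movement from 66.2% onward could appear as a rise within one curve.

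**Which rule causes what.** Non-responder imputation within the open-label treated set would still give 45/68 = 66.2% at Week 24, because the double-blind leavers are not in that set. It would stop only the later drift. Restoring 60.0% needs the full randomized and treated denominator.

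**Rescue.** Rescued subjects continue into open label (Protocol 3.1.5). If 3 rescued placebo subjects met DOI at Week 24 and were counted, with 7 leavers per arm, placebo would be 28/68 = 41.2% and the difference 25.0 points.

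**Japan.** SAP 7.1 contemplates about 10 Japanese subjects per arm. Illustratively, 6/10 = 60% becomes 6/8 = 75% if two non-responders leave.

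**The case against.** The strongest reply is that the Week 52 rate is a descriptive summary in an explicitly defined subset, without p-values or formal testing, and so cannot contradict or alter the primary result. That stands. A reader might infer that the later report undermines the primary analysis, and the documents do not support this. The two figures would even agree if every subject entered open label with observed data and rescue were handled alike.

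A reader might also infer that the rates must rise. They need not: completers who do not enter open label are a recognised category (SAP 7.3.1), and if enough of them are responders the rate falls, as shown above.

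Nor do the documents establish that the later reports have no rescue rule. The inherited endpoint in SAP 4.1 is DOI without rescue, while the explicit non-response rule sits in SAP 7.5.2, which is not inherited. The text is ambiguous, not silent.

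Discontinuations and their reasons are tabulated separately by randomized group (SAP 11.4.1 and 11.5.2), so attrition is partly disclosed. Section 11.2 and parts of 7.5 and 11.6.2 are blacked out, and the DPP that details selected outputs is not available. So I can say only that the visible text plans no non-responder version; whether n per visit will be displayed is unknown. These points lower the weight of the concern. They do not remove the selection built into the stated rule.

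**Conclusion.** The point holds as a cheap improvement. By the stated rules, the Week 52 and Week 76 reports will generally carry a Week 24 DOI rate different from the primary one, chiefly because of the population restriction and secondarily because of the missing-data rule and the unclear handling of rescue. Later rates can drift as the denominator shrinks, probably upward given who the protocol requires to leave, but not certainly.

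The sizes above rest on assumed losses and, except where stated, on all leavers being non-responders. The direction of any change in the between-arm difference cannot be predicted.

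The point is limited to responder proportions at Weeks 52 and 76. The mixed models deal with missing data under missing-at-random, and Section 11.6 plans no efficacy analysis for the long-term extension.

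**What to change.** Before the Week 52 and Week 76 outputs are finalised:

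1. Add a table of DOI over time with non-responder imputation on a fixed denominator: all randomized and treated subjects for Week 52, and all Japanese randomized and treated subjects for Week 76. The open-label treated set is not enough, since it leaves the Week 24 gap in place.
2. State that the primary rescue rule applies to the double-blind visits in these reports.
3. Keep the as-observed rates as a supplement, labelled as such, with n/N at each visit.
4. Name the primary analysis as the Week 24 DOI rate for efficacy conclusions.

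The cost is one extra table per report, with no new data. The rates will probably look less favourable, and non-responder imputation will count as failures some leavers who may still be responding, which is why the as-observed table should stay alongside it.

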11.6.1 Other Efficacy Analyses

IMACS DOI

Proportion of subjects in IMACS DOI over time during the study will be presented by the double-blind treatment groups and visit. Point estimate of response rate, 95% CI, point estimates and 95% CI of treatment difference adjusted for randomization stratification factors: disease diagnosis (DM vs. Non-DM), ILD (absent vs present), Region (Japan vs ROW) (based on minimum risk weights).

Proportion of subjects who meet the $\geq 20\%$ improvement from baseline over time for each of the core measures of IMACS (PGA, SGA, MMT-8, HAQ-DI, MDAAT and muscle enzymes) will be presented by double-blind treatment groups and visit. Point estimate of response rate, 95% CI, point estimates and 95% CI of treatment difference adjusted for randomization stratification factors: disease diagnosis (DM vs. Non-DM), ILD (absent vs present), Region (Japan vs ROW) (based on minimum risk weights).

The proportion of subjects in IMACS Minimal, Moderate and Major responses using the Myositis Response Criteria tool (as defined in [section 8.1.11](#)) will also be presented over time during the study. Point estimates and 95% CI within each treatment group for IMACS Minimal, Moderate and Major DOI response will be provided by visit. Differences in IMACS Minimal, Moderate and Major DOI response rates between the double-blind treatment groups will be provided by point estimate and corresponding 95% CIs based on an ordinal logistic regression model.

Additional separate longitudinal repeated mixed effects models will be used to assess the mean change from baseline over time in the study in each of the IMACS core measures (PGA, SGA, MMT-8, HAQ-DI, MDAAT and muscle enzymes). The mixed models will include double-blind treatment group, baseline measurement, randomization stratification factors: disease diagnosis (DM vs. Non-DM), ILD (absent vs present), Region (Japan vs ROW), time (study days in which each core measure was collected), time by baseline measurement and time by treatment interactions as fixed effects and subject as a random effect. Adjusted mean, SE, 95% CI for adjusted mean difference between treatment groups will also be provided. The estimate of baseline mean core measure, mean post-baseline core measure, and adjusted mean change from baseline core measure will be also be presented by double-blind treatment group and visit.

